### 3. PARTICIPANT SELECTION

#### 3.1 Eligibility Criteria

Unless otherwise specified, laboratory tests required for eligibility must be completed within 28 days prior to start of protocol therapy. Baseline tumor measurements by CT scan must be performed within approximately 4 weeks (28 days) of starting study treatment. Bone marrow biopsy within approximately 12 weeks (90 days) prior to study treatment will be acceptable if there has not been a significant change to the anti-cancer therapy given since the test was performed.

Participants must meet the following criteria on screening examination to be eligible to participate in the study:

- Serum aspartate transaminase (AST) and alanine transaminase (ALT)  $\leq 3.0$  x local upper limit of normal (ULN), bilirubin  $\leq 1.5$  x local ULN (unless bilirubin rise is due to Gilbert's syndrome or of non-hepatic origin)
- 3.1.7 Adequate renal function as defined as:
- Serum creatinine  $\leq 1.5$  times the local upper limit of normal or creatinine clearance  $\geq 50$  mL/min using a 24-hour urine collection
- 3.1.8 Women of child-bearing potential and men must agree to use adequate contraception (hormonal, barrier method or abstinence) prior to study entry, for the duration of study participation, and for 3 months after the last dose of duvelisib. Male subjects must also refrain from donating sperm during their participation during the study and for 3 months after the last dose of duvelisib. Effective methods of contraception include:
- True abstinence: When this is in line with the preferred and usual lifestyle of the subject.
    - Periodic abstinence (e.g., calendar, ovulation, symptothermal, post-ovulation methods), and withdrawal are not effective methods of contraception.
  - Sterilization
    - Female subject or female partner of male subject: When a woman of childbearing potential has had surgical bilateral oophorectomy (with or without hysterectomy) or tubal ligation at least 6 weeks prior to starting treatment. In case of oophorectomy alone, only when the reproductive status of the woman has been

CONFIDENTIAL

This document is confidential. Do not disclose or use except as authorized.

confirmed by follow up hormone level assessment would they be eligible to begin treatment

- Male subject or male partner of female subject: (with the appropriate post-vasectomy documentation of the absence of sperm in the ejaculate).
- Placement of an intrauterine device (IUD) or intrauterine system (IUS).
- Hormonal methods of contraception associated with inhibition of ovulation: oral, implantable, injectable, intravaginal, or transdermal contraception

3.1.9 Negative serum human chorionic gonadotropin (hCG) pregnancy test within 7 days before first dose of study intervention if the subject is a woman of childbearing potential.

3.1.10 Ability to understand and the willingness to sign a written informed consent document

### **3.2 Exclusion Criteria**

3.2.1 Previous treatment with venetoclax or duvelisib (prior venetoclax allowed for RS patients and for CLL/SLL patients if they have been off venetoclax therapy for at least one year prior to enrollment)

3.2.2 Patients receiving cancer therapy (i.e., chemotherapy, radiation therapy, immunotherapy, biologic therapy, surgery within 2 weeks of Cycle 1/Day 1 with the following exceptions:

- For patients on targeted therapies, a washout of least five half-lives is required
- Patients who experience clinical deterioration may start therapy after a shorter washout period with prior approval by the PI
- Corticosteroid therapy (prednisone or equivalent  $\leq 20$  mg daily) is allowed

3.2.3 Confirmed central nervous system involvement

3.2.4 Allogeneic hematologic stem cell transplant within 6 months of starting study treatment or active graft vs. host disease (GVHD) requiring treatment or prophylaxis

3.2.5 Administration of live or live attenuated vaccine within 6 weeks of initiation of therapy

3.2.6 Unable to receive prophylactic treatment for pneumocystis, herpes simplex virus (HSV), or herpes zoster (VZV) at screening

3.2.7 Ongoing treatment with chronic immunosuppressants (e.g., cyclosporine)

3.2.8 Active malignancy other than CLL/SLL or RS requiring therapy with the exception of hormonal therapy, non-melanoma skin cancer or carcinoma in situ of the cervix, bladder cancer, or prostate cancer not requiring treatment. Subjects with previous malignancies are eligible if they have been disease-free for 2 years or more.

CONFIDENTIAL

This document is confidential. Do not disclose or use except as authorized.

- 3.2.9 Any active systemic infection requiring IV antibiotics or uncontrolled, active infections
- 3.2.10 Active Human immunodeficiency virus (HIV), hepatitis C virus (HCV), or hepatitis B virus (HBV)
- Subjects with a positive hepatitis B surface antigen [HBsAg] or hepatitis C antibody [HCV Ab] will be excluded
  - Subjects with a positive hepatitis B core antibody (HBcAb) must have negative hepatitis B virus (HBV) deoxyribonucleic acid (DNA) to be eligible, must receive prophylaxis with entecavir (or equivalent) concomitant with duvelisib treatment, and must be periodically monitored for HBV reactivation by institutional guidelines
  - Investigators who believe that a positive HBcAb is false due to passive immunization from previous immunoglobulin infusion therapy should consider the risk-benefit for the patient given the potential for reactivation
- 3.2.11 Major surgery within 4 weeks of first dose of study drug
- 3.2.12 Currently active gastrointestinal disease, including colitis, inflammatory bowel disease and diarrhea requiring therapy
- 3.2.13 Currently active, clinically significant cardiovascular disease, such as uncontrolled arrhythmia or Class 3 or 4 congestive heart failure as defined by the New York Heart Association Functional Classification; or a history of myocardial infarction, unstable angina, acute coronary syndrome, stroke, or sustained ventricular arrhythmia within 6 months of first dose of study drug
- 3.2.14 Any life-threatening illness, medical condition, or organ system dysfunction that, in the investigator's opinion, could compromise the subject's safety or put the study outcomes at undue risk
- 3.2.15 Use of Coumadin for anticoagulation (other anticoagulants permitted)
- 3.2.16 Lactating or pregnant
- 3.2.17 Concurrent administration of medications or foods that are strong inhibitors or inducers of CYP3A (see Appendix D) . The concomitant use of drugs or foods that are strong or moderate inhibitors or inducers of CYP3A are not allowed beginning 1 week prior to the first dose of duvelisib.

CONFIDENTIAL

This document is confidential. Do not disclose or use except as authorized.

- 3.2.18 Patients with ongoing use of prophylactic antibiotics are eligible as long as there is no evidence of active infection and the antibiotic is not included on the list of prohibited medications
- 3.2.19 Unable to swallow capsules or malabsorption syndrome, disease significantly affecting gastrointestinal function, or resection of the stomach or small bowel, symptomatic inflammatory bowel disease or ulcerative colitis, or partial or complete bowel obstruction resulting in malabsorption or chronic diarrhea
- 3.2.20 History of chronic liver disease or veno-occlusive disease/sinusoidal obstruction syndrome
- 3.2.21 History or concurrent condition of interstitial lung disease of any severity and/or severely impaired lung function
- 3.2.22 Active abuse of alcohol or illicit drug use
- 3.2.23 Known hypersensitivity to duvelisib and/or its excipients
- 3.2.24 History of tuberculosis treatment within the 2 years prior to initiation of therapy

### **3.3 Inclusion of Women and Minorities**

Both men and women of all races and ethnic groups are eligible for this trial.

CONFIDENTIAL

This document is confidential. Do not disclose or use except as authorized.

## 4. REGISTRATION PROCEDURES

### 4.1 General Guidelines for DF/HCC Institutions

Institutions will register eligible participants in the Clinical Trials Management System (CTMS) OnCore. Registrations must occur prior to the initiation of any protocol-specific therapy or intervention. Any participant not registered to the protocol before protocol-specific therapy or intervention begins will be considered ineligible and registration will be denied.

An investigator will confirm eligibility criteria and a member of the study team will complete the protocol-specific eligibility checklist.

Following registration, participants may begin protocol-specific therapy and/or intervention. Issues that would cause treatment delays should be discussed with the Overall Principal Investigator (PI). If the subject does not receive protocol therapy following registration, the subject must be taken off-study in the CTMS (OnCore) with an appropriate date and reason entered.

### 4.2 Registration Process for DF/HCC Institutions

Applicable DF/HCC policy (REGIST-101) must be followed.

### 4.3 General Guidelines for Other Investigative Sites

Eligible participants will be entered on study centrally at Dana-Farber Cancer Institute by the lead site project manager. All sites should call the project manager to verify dose level and or slot availabilities.

Following registration, participants should begin protocol therapy as soon as feasible. Issues that would cause treatment delays should be discussed with the Overall PI. If the subject does not receive protocol therapy following registration, the subject must be taken off-study in the CTMS (OnCore) with an appropriate date and reason entered.

### 4.4 Registration Process for Other Investigative Sites

To register a participant, the following documents should be completed by the research nurse or data manager and faxed or e-mailed to the lead site project manager.

- Copy of relevant medical records that support the items on the eligibility checklist (with PMI redacted)
- Participant consent form signed by both the consenting physician investigator, and the participant
- HIPAA authorization form (if applicable)
- Completed eligibility checklist

CONFIDENTIAL

This document is confidential. Do not disclose or use except as authorized.

The participating site will e-mail the lead site project manager to verify eligibility. The project manager will follow DF/HCC policy (REGIST-101) and register the participant on the protocol. The lead site project manager will email the participant study number, and if applicable the dose treatment level, to the participating site. The lead site may also contact the participating site and verbally confirm registration.

[figure not shown]
CONFIDENTIAL

This document is confidential. Do not disclose or use except as authorized.

## 5. TREATMENT PLAN

**Figure 2: Phase I dosing algorithm**

**Phase I: 3 + 3 dose escalation**

In the phase I portion of the study, patients will start with 25 mg BID of duvelisib for seven days. A traditional 3 + 3 design will be used to accrue patients to one of three dose levels of venetoclax, which will start on day 8 and will be given in combination with duvelisib. The starting dose level of venetoclax will be 100 mg daily (dose level +1) with escalation to 200 mg daily (dose level +2) and to 400 mg daily (dose level +3). De-escalation to 50 mg daily (dose level -1) will be performed if unexpected toxicity is observed. Patients will be admitted for initial dosing at the initial dose and at each dose escalation of venetoclax during the dose ramp-up for close monitoring for tumor lysis syndrome (TLS).

At each dose level, patients be treated with 10 mg of venetoclax for one week, followed by a weekly dose ramp-up of venetoclax as per the label, with patients in the initial dosing cohort

CONFIDENTIAL

[figure not shown]
This document is confidential. Do not disclose or use except as authorized.

stopping at a lower dose of venetoclax than the approved dose of 400 mg. Patients will continue combination therapy for a total of one year, followed by venetoclax monotherapy until the time of disease progression without clinical benefit, death, unacceptable toxicity, withdrawal of consent, or physician/patient discussion of discontinuation based on objective disease response.

Once the MTD of venetoclax in combination with duvelisib is determined, 3 additional patients will be accrued at that dose level who will start with venetoclax 20 mg and have a dose ramp up identical to the other patients in that cohort. Also, patients assigned to lower dose levels in the phase I portion of the trial will have the option to escalate their venetoclax dose to the MTD.

**Phase II:**

**Figure 3: Phase II Dosing algorithm**

The phase II portion of the study will be designed in two stages. Patients will undergo a dose-ramp up venetoclax as described in the phase I trial, with the exception that since there was no evidence of TLS in patients at 10 mg during phase I, participants in phase II will have the option of starting their dose ramp up at 20 mg of venetoclax for one week, followed by a weekly dose ramp-up to 400 mg daily. Patients who wish to start at 20 mg venetoclax will be required to do so inpatient for the first 2 dose ramp-ups (at 20 mg and 50 mg) and can then do the remaining ramp-ups (i.e. to 100, 200, and 400 mg) as an outpatient.

Patients who are low- or medium risk for TLS and wish to be treated all in the outpatient setting will have to start at 10 mg and then the following week go up to 20 mg, and then complete the rest of the usual ramp-up to 50 mg, 100 mg, 200 mg, and 400 mg.

High risk patients will be hospitalized for the initial dose ramp-ups, but will have the option to start at 10 or 20 mg. If they start at 10 mg then they will need to be hospitalized for the first 3 dose ramp-ups (10 mg, 20 mg, and 50 mg), or for the first two dose ramp ups ( 20mg and 50mg) if they start at 20 mg.

**Accelerated ramp up for RS patients:**

CONFIDENTIAL

This document is confidential. Do not disclose or use except as authorized.

Given the potential for rapidly progressive RS, these RS patients will also have the option to undergo an accelerated venetoclax ramp-up in the inpatient setting modeled after another study of venetoclax plus chemotherapy that was recently reported ([name] et al., ICML, 2019). In that study, venetoclax was safely ramped up in a daily fashion for 20 RS patients, who were monitored closely in the inpatient setting, with no evidence of tumor lysis syndrome. The venetoclax is dosed at 20 mg for day 1, and if no TLS is observed on labs done 6-8 hours and 24 hours later, then the dose is ramped up to 50 mg on day 2, 100 mg on day 3, 200 mg on day 4, and 400 mg on day 5 if the daily labs done 6-8 hours and 24 hours later continue to show no TLS. If laboratory TLS does occur, the next day's dose will be held until there is improvement in the TLS, at which point escalation to the next dose may occur

Study visits will occur weekly through cycles 1-2, once per cycle during cycles 3-7, every two cycles from cycle 7-13, and every 3 cycles thereafter through cycle 60. After cycle 60, patients will return for study visits every six cycles until they are removed from treatment. Patients will be treated with duvelisib plus venetoclax for up to one year followed by venetoclax monotherapy until disease progression without clinical benefit, death, unacceptable toxicity, withdrawal of consent, physician/patient discussion of discontinuation based on objective disease response, or they elect to go on a new CLL or Richter's directed therapy.

CT of the neck, abdomen, pelvis and neck (CLL) or full body PET/CT (Richter's) scans will be mandatory at C4D1, C7D1, C13D1, and then at the discretion of the treating investigator or approximately every six cycles thereafter. Bone marrow biopsy will be mandatory at study entry and at the C7D1, C13D1, and C25D1 re-staging visits. Subsequent bone marrow biopsies will be performed as clinically indicated thereafter at the discretion of the treating investigator.

Patients will be evaluated for MRD negativity in the peripheral blood approximately every three months and with each bone marrow biopsy (except the baseline biopsy). MRD testing will be performed by 4-color flow cytometry with a sensitivity of  $10^{-4}$  and when possible also by ClonoSEQ (Adaptive), a next generation sequencing technology.

If after at least one year of treatment, a patient achieves a complete remission (CR) or complete remission with incomplete count recovery (CRi) with MRD-negativity in the marrow, they will have the option to discontinue venetoclax. Patients with a PR with MRD-negativity will have the option of discontinuing venetoclax after 24 months of treatment. Those that come off treatment for this reason will be monitored for disease recurrence with peripheral blood MRD testing by flow cytometry approximately every 3 months. Patients who have detectable recurrence (at minimum, confirmed by two successive peripheral blood MRD positive assessments) in the peripheral blood will have the option to restart venetoclax.

In the event that patients need to restart venetoclax due to disease recurrence, they will be re-staged. If they have MRD-detectable disease but no other evidence of clinical disease progression, venetoclax can be resumed at 400 mg daily in the outpatient setting with TLS monitoring 6-8 and 24 hours after the initial dose. Patients with evidence of clinical disease progression on the re-staging evaluation will be treated with a venetoclax dose ramp up as per the label, starting with 20 mg daily and escalating to 400 mg daily. Prophylaxis against and

CONFIDENTIAL

This document is confidential. Do not disclose or use except as authorized.

treatment of TLS will be performed as during initial therapy. Patients who do not achieve MRD negativity or have disease progression after reaching full dose venetoclax monotherapy have the option to add duvelisib at the highest dose they had previously tolerated and continue it until MRD negativity is achieved on two successive peripheral blood MRD assessments or indefinitely depending on tolerability. Patients who achieve maximal response and are allo transplant candidates can elect to go off study to move on to transplant.

Participants who elect to come off therapy at the time of complete response must have received at least one year of treatment on study.

Those that discontinue duvelisib during combination therapy may continue to receive venetoclax monotherapy.

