### **5.1.2 Venetoclax:**

Venetoclax will be administered daily, with 28 consecutive days defined as a treatment cycle (up to 42 days for cycle 1) until the time of disease progression without clinical benefit, death, unacceptable toxicity, withdrawal of consent, or physician/patient discussion of discontinuation based on objective disease response, or they elect to go on a new CLL or Richter's directed therapy. The first dose of venetoclax will be given on day 8 of cycle 1 at a starting dose of 10 mg. All patients will be admitted for administration of the initial dose of venetoclax at each dose escalation. Patients will be started on allopurinol and IV hydration for TLS prophylaxis. TLS laboratories will be checked approximately 4, 8, 12, and 24 hours post venetoclax dose. Pre-dose laboratory values will be used as baseline to assess for potential electrolyte abnormalities following venetoclax. Patients can be discharged if no evidence of laboratory TLS 24 hours after dosing, according to the Cairo-Bishop criteria for TLS. If laboratory or clinical TLS is seen, as defined by Cairo-Bishop criteria, patients will be managed as per appendix C. Patients will be admitted weekly for each dose escalation (10 mg, 20 mg, 50 mg, 100 mg, 200 mg, 400 mg) for up to six weeks (42 days) depending on the target dose level. The same rules and TLS laboratory evaluations will be applied for each dose escalation, with the potential to escalate to 100 mg (dose level +1), 200 mg (dose level +2), and 400 mg (dose level +3).

CONFIDENTIAL

This document is confidential. Do not disclose or use except as authorized.

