### 5.2.2 Ramp-up cycles Day 1 of combination duvelisib and venetoclax therapy:

- ANC must be  $\geq 500/\text{mm}^3$  (growth factor support allowed), unless they have significant bone marrow involvement of CLL confirmed on pretreatment biopsy
- Platelet count must be  $\geq 20\text{K}$  (transfusion support allowed), unless they have significant bone marrow involvement of CLL confirmed on pretreatment biopsy
- Serum creatinine must be  $\leq 1.5$  times the upper limit of normal or creatinine clearance must be  $\geq 50 \text{ mL/min}$  using a 24-hour urine collection
- All non-hematologic toxicities must have resolved to  $\leq$  Grade 2, or to the patient's baseline condition
- No evidence of active tumor lysis syndrome

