- Chemistry laboratory tests must be performed STAT at least at the following time points: pre-dose (within 4 hours before venetoclax administration), and approximately 4, 8, 12, and 24 hours after the first dose of venetoclax at 10 mg and each subsequent dose escalation. Pre-dose laboratory values will be collected and used as baseline to assess potential electrolyte abnormalities occurring post venetoclax administration.
- If any laboratory changes in potassium, uric acid, phosphate, calcium, lactate dehydrogenase, or creatinine are observed within the first 24 hours after initiation of dosing, see Appendix C (Recommendations for Initial Management of Electrolyte Abnormalities and Prevention of Tumor Lysis Syndrome [TLS]) for additional laboratory assessments and management guidelines.
- Patients without evidence of TLS can be discharged 24 hours following venetoclax administration

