#### 5.4.2 Treatment of TLS:

All subjects meeting criteria of laboratory TLS or  $\geq$  grade 1 TLS according to the Cairo-Bishop Definition of Tumor Lysis Syndrome (see Appendix B) should receive vigorous intravenous hydration, aggressive electrolyte management, and should be considered for rasburicase therapy as needed to reduce hyperuricemia, until correction of electrolyte abnormalities. See Section 6, Dose Modification, for additional instructions.

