### 7.3.1 Common AEs Associated with Venetoclax

#### 7.3.1.1 Tumor Lysis Syndrome (TLS)

TLS, including fatal events and renal failure requiring dialysis, has occurred in previously treated CLL patients with high tumor burden when treated with venetoclax. Venetoclax can cause rapid reduction in tumor and thus poses a risk for TLS in the initial ramp-up phase. Changes in blood

CONFIDENTIAL

This document is confidential. Do not disclose or use except as authorized.

chemistries consistent with TLS that require prompt management can occur as early as 6 to 8 hours following the first dose of venetoclax and at each dose increase. The risk of TLS is a continuum based on multiple factors, including tumor burden and comorbidities. Reduced renal function further increases the risk. Patients should be assessed for risk and should receive appropriate prophylaxis for TLS, including hydration and anti-hyperuricemics. Blood chemistries must be monitored closely and abnormalities must be managed promptly. Dosing can be interrupted if needed and more intensive measures (intravenous hydration, frequent monitoring, hospitalization) can be employed as overall risk increases. Concomitant use of venetoclax with strong or moderate CYP3A inhibitors and P-gp inhibitors increases venetoclax exposure and may increase the risk of TLS.

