## APPENDIX C: MANAGEMENT OF TUMOR LYSIS SYNDROME

Abnormality	Management Recommendations
Hyperkalemia (Including Rapidly Rising Potassium) (continued)	
Potassium $\geq$ 6.0 mmol/L (6.0 mEq/L) and/or symptomatic (e.g., muscle cramps, weakness, paresthesias, nausea, vomiting, diarrhea)	
 
• Perform STAT ECG and commence telemetry.
 
• Nephrology (or other acute dialysis service) assessment with consideration of initiating dialysis.
 
• Administer Kayexalate 60 g (or Resonium A 60 g).
 
• Administer furosemide 20 mg IV <math>\times</math> 1 (or higher dose as needed)
 
• Administer insulin 0.1 U/kg IV + D25 2 mL/kg IV.
 
• Administer sodium bicarbonate 1 to 2 mEq/kg IV push.
 
• If sodium bicarbonate is used, rasburicase should not be used as this may exacerbate calcium phosphate precipitation.
 
• Administer calcium gluconate 100 to 200 mg/kg IV slowly if there is ECG/telemetry evidence of life-threatening arrhythmias. Do not administer in same IV line as sodium bicarbonate.
 
• Recheck potassium, phosphorus, uric acid, calcium and creatinine every hour STAT until improvement observed.
 

Hyperuricemia	
Uric acid $\geq$ 8.0 mg/dL (476 $\mu$ mol/L)	
 
• Consider rasburicase (6 mg IV <math>\times</math> 1 or as per institutional standard).                             
 
○ If rasburicase is used, sodium bicarbonate should not be used as this may exacerbate calcium phosphate precipitation.
 
 
 
• Recheck potassium, phosphorus, uric acid, calcium and creatinine in 1 hour STAT.
 

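### In the accelerated RS ramp-up, a patient with laboratory TLS may go to the next venetoclax dose on undefined improvement, while a patient without TLS needs labs that show none

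*Combined protocol and SAP*

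**What the plan says.** The accelerated schedule gives venetoclax 20, 50, 100, 200 and 400 mg on five successive days. The same rule stands in four places: the Synopsis, Section 5 (Accelerated ramp up for RS patients), Section 5.1.2 and Section 5.1.2.2.

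- **No TLS.** The first step needs clear labs at both time points after the 20 mg dose. Later steps are allowed "if the daily labs done 6-8 hours and 24 hours later continue to show no TLS".
- **Laboratory TLS.** The next day's dose is "held until there is improvement in the TLS, at which point escalation to the next dose may occur". No laboratory value, resolution, repeat of the same dose or minimum observation time is required.

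Section 5.1.2.2 adds that the Overall PI or a delegate must approve the accelerated schedule in writing before venetoclax is started. It asks for no approval before escalation after TLS.

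Three other places bear on dosing after TLS:

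- Section 5.2.2, headed as criteria for Day 1 of ramp-up cycles, lists "No evidence of active tumor lysis syndrome".
- Section 6.2 allows, but does not require, venetoclax to be cut by 50% at a time for TLS.
- Table 5 in Section 6.2.2 recommends holding venetoclax for Grade 2 and 3 non-hematologic toxicity until grade 1 or lower (or, at Grade 3, baseline). It then resumes at the same level after Grade 2 and one level lower, if indicated, after Grade 3. Departures are to be discussed with the PI.

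Section 5.4.2, on treating laboratory or clinical TLS, sends the reader to Section 6. The accelerated ramp-up text cites neither Section 5.2.2 nor Section 6.

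**The concern.** The written test for going up is weaker for the patient who has just shown TLS than for the patient who has not. The protocol's own account of the risk makes this matter. Section 7.3.1.1 reports fatal TLS and renal failure requiring dialysis with venetoclax, and says that the blood changes "can occur as early as 6 to 8 hours following the first dose of venetoclax and at each dose increase".

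The support cited for the daily schedule does not reach this situation. The model study is described as having seen no TLS in 20 RS patients, so as described it holds no experience of escalating after TLS. It also paired venetoclax with chemotherapy, not duvelisib. The trial's own reassurance, no TLS in phase I, comes from a weekly ramp-up starting at 10 mg.

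Section 2.5 notes a potential interaction between the two study drugs through CYP3A4. Section 5.4.6 calls duvelisib a moderate CYP3A4/5 inhibitor, and Section 7.3.1.1 says that moderate inhibitors raise venetoclax exposure and may raise TLS risk. Section 13.2 gives the RS cohort no early stopping rule for toxicity, so the patient-level rule carries more of the weight.

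**Working it through.** The plan gives no figure for this rule, so there is none to reproduce. The main check is a comparison of texts.

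**1. Which other TLS rules are true comparators.** Some only look like comparators. Section 5.1.2 says "Patients can be discharged if no evidence of laboratory TLS 24 hours after dosing", and Section 5.4.1 is similar; both govern leaving hospital. Section 5.4.2 continues supportive care "until correction of electrolyte abnormalities"; that governs treatment. None of these says when dosing may resume. The comparators that bear on dosing are Section 5.2.2, Section 6.2 and Table 5.

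**2. Section 5.2.2 has two readings.** If its TLS criterion applies at every dose step, it bars escalation during active TLS and contradicts the accelerated text. If it applies only on Day 1, as its heading suggests, it does not cover the daily steps. Either reading calls for an edit.

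**3. Section 6 points to a stricter course but does not settle it.** Table 5 is recommended guidance and Section 6.2 is permissive. Table 5 also runs by grade, while Appendix B grades clinical TLS only. The specific sentence in the accelerated text can be read as overriding both.

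**4. Illustration (assumed values).** Potassium falls from 6.6 to 6.2 mmol/L. That is an improvement. It is still above the 6.0 mmol/L level in Appendix B, at which Appendix C also calls for a dialysis-service "assessment with consideration of initiating dialysis". The accelerated text would not stop escalation.

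**5. Size of the step allowed.** 50/20 = 2.5; 100/50 = 200/100 = 400/200 = 2. TLS first seen at 400 mg does not trigger the rule, because no higher dose follows.

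**6. How many patients might enter the TLS branch.** Inputs: 0 of 20 with TLS in the model study (Section 5) and 20 RS patients planned (Section 13.2).

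- One-sided 95% upper limit for 0 of 20: 1 − 0.05^(1/20) = 0.139. As a bound, 0.139 × 20 = 2.8 patients if all 20 use the option.
- Chance that at least one patient has laboratory TLS: 1 − (1 − p)^n, with p assumed.

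| p | n = 20 | n = 10 |
|---|---|---|
| 1% | 18% | 10% |
| 5% | 64% | 40% |
| 10% | 88% | 65% |

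- Section 2.3 gives 1 of 60 with laboratory findings in the weekly 20 mg CLL ramp-up. At that rate, 1 − (59/60)^20 = 29%. The rate does not transfer directly to RS or to daily steps.

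These are chances of any laboratory TLS. They are not chances of escalation during unresolved TLS, or of harm.

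**7. Speed kept if resolution is required.** Weekly from 20 mg, the first 400 mg dose falls on venetoclax day 1 + 4 × 7 = 29. Accelerated, it falls on day 5, a gain of 29 − 5 = 24 days. With 1 to 3 extra days in total (assumed), 400 mg is reached on day 6 to 8. The gain is then 23 to 21 days, or 23/24 = 96% to 21/24 = 88% of the original.

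**The case against.** The strongest reply is that the accelerated text does not stand alone. Section 5.4.2 covers every patient with laboratory TLS and points to Section 6, where a 50% reduction is available and Table 5 recommends a hold to grade 1 or baseline. The TLS branch itself imposes a hold that the other branch does not, and then only permits escalation. The patient is in hospital, the PI has approved the schedule, and at the potassium level in the illustration Appendix C calls for an urgent ECG, telemetry and hourly labs. With median survival of 8 to 14 months in clonally related RS (Section 2.2), leaving room for speed is a defensible choice.

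Much of this stands, and it limits the point. A reader might infer that the protocol has no stricter rule for TLS anywhere, or that it directs escalation during active TLS. Neither is supported: Section 6 is stricter, and the sentence is permissive after a mandatory hold. A reader might also take the discharge and supportive-care rules as contradicting the escalation rule. They do not, since an inpatient can be unfit for discharge and still be dosed under a separate rule. Nor do the documents establish an interaction between the two study drugs; Section 2.5 speaks only of potential. The most serious early TLS described in Section 2.3 followed starting doses of 50 mg or more, above the 20 mg used here.

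What the reply does not remove is the wording. Improvement short of resolution meets the stated condition, the text does not send the investigator to the stricter guidance, and PI approval comes before any TLS has been seen.

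**Conclusion.** The point holds as an inconsistency in a stated dosing rule. After laboratory TLS and a hold, the accelerated RS text permits a 2- to 2.5-fold dose increase on undefined improvement. That is looser than the test for patients without TLS and looser than the recommended Section 6 guidance. It conflicts with Section 5.2.2 if that criterion covers each step; if it does not, the accelerated text has no explicit requirement for resolution.

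The size is limited and partly unknown. The option is open to at most 20 planned RS patients, and the plan does not say how many will use it. The 13.9% is an upper bound from 0 of 20, on the assumption that the model study's rate applies; it is not an estimate. A reader might take the 18% to 88% range as the risk of unsafe escalation. It is only the chance of at least one laboratory TLS in 20 patients at assumed rates of 1% to 10%. The RS efficacy rule (7 or more complete responses in 20) and its operating characteristics are unaffected. This is a safety-wording correction worth making because it is cheap.

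**What to change.** - In the Synopsis and Sections 5, 5.1.2 and 5.1.2.2, replace the sentence on laboratory TLS with: the next dose is held until laboratory TLS (Appendix B) has resolved, and the patient goes up only once TLS labs show no TLS. Add a cross-reference to Section 6.
- In Section 5.2.2, state that the no-active-TLS criterion applies at every venetoclax ramp-up step, including the daily steps of the accelerated schedule.
- If the sponsor wants earlier escalation for rapidly progressive RS, write it as an explicit exception to Section 5.2.2 and give the laboratory values that qualify.

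This is one amendment, changing four copies of a sentence and one criterion, with no new patients or assays. Patients without TLS are unaffected. Those with laboratory TLS wait longer, by an assumed 1 to 3 inpatient days with repeat labs. The documents give no source for that delay.
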